Further evidence of the safety and tolerability of pregnenolone comes from a recent study by [name] (consultant) in 120 patients (n=38 women) with schizophrenia given 500 mg of pregnenolone or placebo for eight weeks (data reported with permission from [name]). The number of participants experiencing treatment-emergent adverse events was comparable in the placebo and pregnenolone groups (58% vs. 55%, respectively). Moderate-intensity adverse events were reported by 8.3% of participants in the placebo group and 13.3% of participants in the pregnenolone group. No participants in either group reported adverse events of severe intensity. Three participants in the pregnenolone group and none in the placebo group had serious adverse events (SAEs); no SAEs were related to pregnenolone. Study medication was discontinued in only one participant (secondary to reasons unrelated to study drug).

As mentioned above, pregnenolone appears to increase levels of progesterone. Marx et al. reported a mean increase in progesterone from 0.38 ± 0.15 ng/ml to 2.17 ± 0.64 ng/ml in patients with schizophrenia given pregnenolone for eight weeks at the dose proposed in the current application. Eight of these nine participants were men. Thus, the impact of pregnenolone on progesterone in women is not well studied. The mean progesterone level achieved during pregnenolone administration in this study was higher than is typical for men (0.3-1.2 ng/ml), postmenopausal women (<0.7 ng/ml) or premenopausal women during the follicular phase (0.2-1.2 ng/ml), but lower than during the luteal phase (3.3-25.0 ng/ml). Oral contraceptives containing the combination of progestin (a synthetic progesterone) AND estradiol were shown in the Women's Health Initiative, following several years of treatment, to increase the risk of deep vein thrombosis, pulmonary embolism, myocardial infarction, breast cancer and dementia in postmenopausal women (Rossouw et al., 2002). **Therefore, we have excluded persons at an elevated risk, based on personal and family history for any of these disorders, and also exclude women over 62 years of age.**

Because it is theoretically possible that pregnenolone may have interactions with oral contraceptive agents, **we will exclude patients taking these medications but include participants using other forms of birth control.** This is a precautionary procedure for a research study.

Although pregnenolone is available without a prescription, we do not feel that it is ethical, given the current state of our knowledge, to recommend long-term treatment with this agent. The primary risk of discontinuing the study drug (assuming it is effective) is the risk of recurrence of depressive symptoms (tapering schedule is described in section 11 below). The risks of continuing the pregnenolone long-term are not known yet.

Pregnenolone will be purchased from a supplier (MEDISCA) the UTSW researchers have used in prior research studies. MEDISCA is a leading FDA-registered supplier of quality pharmacy compounding products. A certificate of analysis will be provided documenting the content of the sample. In addition, pregnenolone and other neurosteroids serum levels will be assessed at baseline and after pregnenolone or placebo exposure. Although pregnenolone is made by the human body, commercially available products are synthesized like other drugs and not extracted from natural sources. Diosgenin ($3\beta,25R$)-spirost-5-en-3-ol) is typically used in the commercial synthesis of pregnenolone, progesterone, cortisone and other compounds containing a steroid nucleus. Study medication and identical placebos will be prepared at the UTSW site by Abrams Royal Pharmacy, a Dallas compounding pharmacy we have used in numerous studies, and at the MGH site by Johnson Compounding and Wellness, a local compounding pharmacy with experience in supplying medication for research studies. The filler will be lactose or sodium bicarbonate. Abrams Royal Pharmacy is a member of the International Academy of Compounding Pharmacies and the Professional Compounding Centers of America.

Risks to an Embryo, Fetus, or Breast-fed Infant: Pregnant or breastfeeding women, as well as women planning pregnancy will be excluded from the study. A negative urine pregnancy test will be mandated before a woman of child-bearing potential can participate in this study, as well as recurrently throughout the study in case a pregnancy is suspected. Women who do not agree to use an acceptable form of birth control (as outlined in the inclusion/exclusion criteria) will not be enrolled in the study. The risks to embryo/fetus/breast-fed infant will be clearly outlined in the consent form for the participant.

Physiological Measures: Risks associated with drawing blood from your arm include minimal discomfort and/or bruising. Infection, excess bleeding, clotting, and/or fainting also are possible, although it is unlikely.

Psychological Stress: Mild fatigue, anxiety and discomfort are potential, but are unlikely (20% chance), adverse effects associated with the study. Investigators and staff with extensive experience and expertise, who are sensitive to the needs of participating individuals, conduct clinical and behavioral evaluations. Breaks will be taken in order to minimize fatigue and discomfort, and participants may choose to refrain from answering any questions that induce undue discomfort and may stop study participation at any time.

Loss of Confidentiality: Any time that data is collected; there is the potential for loss of confidentiality. This risk is deemed unlikely (<2% chance) due to the multiple efforts that are in place to ensure that all study information is protected and remains confidential.

Other Risks: It is possible that other unforeseen risks may exist. If at any point, the investigators become aware of another risk, it will be reported immediately to the IRB and appropriate measures will be taken to minimize the new risk.

References for Section 10 (Risks):

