Individuals who contact the research clinic (BL8.224 or the Simches Research Building at MGH) will first be screened over the phone (short 15-minute interview) to determine initial eligibility and will be asked questions about their demographic information, medical and psychiatric history, symptoms, medications, allergies, substance use and smoking history. Individuals who appear to meet initial eligibility after completing the phone screen will be invited to come to the clinic for an in-person eligibility assessment visit (Baseline, Visit 1). Participants who sign the informed consent, meet the inclusion criteria and do not meet any of the exclusion criteria at Baseline will be randomized into the study within 2 days of the Baseline visit using the randomization protocol described in section 3 (Concise Summary of Project). While eligibility as determined by mood assessments, cognitive tasks, and some safety assessments (i.e., Section 7, "Clinically significant laboratory, physical examination) will take between 24-48 hours to be assessed. Once this is complete, the subject will be randomized by the unblinded statistician at UTSW.

If the subject initially seems eligible we will distribute her study medication to her in the Baseline V1, but will instruct her not to use the medication until their eligibility has been officially determined and she receives notification from the study team. If the study medication cannot be distributed to the study subject at V1, it will be sent to her via overnight mail.

The study participation will last 16 weeks, with reassessments during 48-96 hours post baseline (via phone), Weeks 1, 2, 4, 6 (via phone), 8, 48-96 hours post baseline (via phone), 9, 10, 12, 14 (via phone), and 16 (See Assessment Schedule Table below). All visits can be scheduled \pm 2 business days of the timeline set on the assessment schedule. Participants will be paid \$100 at Baseline, Week 8, Week 16, at UTSW (\$50 at MGH), \$50 at Weeks 1, 2, 4, 9, 10, 12, and \$25 at phone calls on Weeks 6 and 14 (at UTSW only) with maximum compensation for the study being \$650 at UTSW and \$390 at MGH. DART transportation passes will also be provided to UTSW participants and parking vouchers for MGH participants.

	Visit 1	Visit 2	Visit 3	Visit 4	Visit 5	Visit 6	Visit 7	Visit 8	Visit 9	Visit 10	Visit 11	Visit 12	Visit 13

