With participant consent at Baseline visit, DNA will be obtained for future analysis. Plasma samples for DNA will be coded and sent to UT Southwestern McDermott Center for Human Growth and Development. Samples will have their DNA banked in a secure freezer with coded identification that will not include any personal identifiers such as the subject's name or date of birth.

6. Criteria for Inclusion of Subjects:

The participants must meet the following criteria:

- Women aged 40-67 years who are perimenopausal or early postmenopausal (within 5 years of the last menstrual period if not surgically postmenopausal), including:
 - Women who have experienced changes in menstrual cycle frequency or duration, and/or physical symptoms indicative of menopausal transition, as determined by clinician
 - Women who are using hormonal IUDs (i.e. brands Mirena and Skyla), with FSH level > 20 mIU/m (as menstrual periods are irregular with IUDs that utilize hormones, making irregular/absent periods difficult to assess as related to the menopausal transition).

- Women with significant menopause-related physical symptoms, indicated by any of the following criteria:
 - Greene Climacteric Scale total scores > 20
 - Greene Climacteric Scale sub-score for vasomotor symptoms >3
 - 5 or more bothersome hot flashes per week (self-reported)
- Women meeting DSM-5 criteria for current major depressive disorder (assessed by the SCID)
- Baseline HRSD score of ≥ 18
- Participant agrees to abstain from disallowed medications (specified in the Excluded Concomitant Medication in Section 7) for the duration of the trial

7. Criteria for Exclusion of Subjects:

The participants must not meet any of the following criteria:

- Vulnerable populations (e.g. pregnant/nursing, severe cognitive or intellectual impairment, incarcerated)
- Pregnancy (determined by urine pregnancy test), intending pregnancy or breast feeding
- Psychiatric disorder other than MDD that is acute and the primary focus of symptom burden or treatment.
- History of bipolar disorder or psychotic disorder
- Current substance use disorder

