- Active coronary artery disease, atrial fibrillation, stroke, deep vein thrombosis, pulmonary embolism or blood clotting disorder
- Any severe, life threatening or unstable medical condition that, based on clinician-judgment, would make participation in the study unsafe or inappropriate

- Personal or first degree family history of known hormone sensitive tumors
- History of allergic reaction or side effects with prior pregnenolone use
- Clinically significant laboratory or physical examination findings
- Concurrent enrollment in another clinical trial

Excluded Concomitant Medications:

- Selective estrogen-receptor modulators (SERMs)
- Hormone replacement therapy
- Hormonal contraceptives, excluding Mirena IUD or other IUD with localized progesterone
- Natural menopause or antidepressant supplements
- Episodic sleep medications (chronic, regular, stable-dose benzodiazepines and hypnotics such as zolpidem, Sonata (Zaleplon), and Lunesta (Eszopiclone) OR sleep-sedating antihistamines such as Unisom (Doxylamine succinate) or diphenhydramine allowed)
- Phytoestrogens
- Soy-based medications or supplements
- Oral systemic corticosteroids (prednisone, dexamethasone, methylprednisolone, etc) with the exception of low-dose nasal steroids and inhaled corticosteroids for asthma

8. Sources of Research Material:

All research materials will be obtained during the time of study participation and will only be used only for research purposes. The data that will be used to answer the primary and secondary aims of the study will be depressive and anxiety symptoms, cognitive rating scales, sleep and hot flash inventories, and quality of life assessments. When the results are published, none of the data will be identifiable with specific participants.

9. Recruitment Methods and Consenting Process:

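### Section 10 says women over 62 are excluded for safety, but Section 6 admits women to 67 and Section 7 sets no age limit

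*Combined protocol and SAP*

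**What the plan says.** Section 10 (Potential Risks, under Pregnenolone Risks) reports that pregnenolone raises progesterone and concedes: "Thus, the impact of pregnenolone on progesterone in women is not well studied". It then cites harms found after several years of progestin with estradiol: venous clots, pulmonary embolism, heart attack, breast cancer and dementia. From these it concludes that persons at raised risk are excluded "based on personal and family history for any of these disorders, and also exclude women over 62 years of age".

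Section 6 (inclusion) reads: "Women aged 40-67 years who are perimenopausal or early postmenopausal (within 5 years of the last menstrual period if not surgically postmenopausal". Section 7 (exclusion) contains no age criterion. Section 4 (Study Procedures) says that consenting participants who "meet the inclusion criteria and do not meet any of the exclusion criteria at Baseline will be randomized into the study".

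All of this is running text of the protocol approved on January 30, 2024. None of it comes from an amendment log.

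**The concern.** The age limit in Section 10 is presented as a consequence of a named hazard, so it reads as a safety measure and not as background. The criteria that decide who is randomized do not contain it. An IRB or DSMB member who reads the risk section would credit a protection that the eligibility rules do not provide, and staff at two sites work from a protocol with two upper ages. At stake are the accuracy of the risk statement and the eligibility of a small, older group. The efficacy comparison is not at stake.

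**Working it through.** The plan offers no calculation on this point, so the check sets the texts side by side.

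**1. Which text governs.** Section 4 randomizes on the inclusion and exclusion criteria, which are Sections 6 and 7. Section 10 is not part of that rule.

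**2. The limits, in whole years of age.**

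| Place | Upper age |
|---|---|
| Section 10 (risks) | 62 |
| Section 6 (inclusion) | 67 |
| Section 7 (exclusion) | none stated |

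Difference: 67 − 62 = 5 years. Ages 63, 64, 65, 66 and 67 satisfy Section 6 and fall in the group that Section 10 calls excluded. Section 6 spans 67 − 40 + 1 = 28 single years of age, so these are 5 of 28. That is a share of the age band, not of participants.

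**3. Who could be in that group.** Section 6 also requires perimenopause or early postmenopause, the latter within 5 years of the last period unless menopause was surgical. A non-surgical postmenopausal woman of 63 needs a last period at 63 − 5 = 58 or later, and one of 67 at 67 − 5 = 62 or later. For surgical menopause the 5-year window is waived. Section 6 does not say whether some other meaning of early postmenopause still applies to these women. The documents give no age distribution, so the number affected cannot be estimated.

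**4. Whether anything else supplies the limit.** Section 7 excludes "Active coronary artery disease, atrial fibrillation, stroke, deep vein thrombosis, pulmonary embolism or blood clotting disorder", uncontrolled hypertension, and "Any severe, life threatening or unstable medical condition that, based on clinician-judgment, would make participation in the study unsafe or inappropriate". Section 4 measures neurosteroids, including progesterone, at Baseline, Week 8 and Week 16. Section 12 provides a DSMB that meets at least twice a year. These reduce or monitor risk, but none sets an age limit.

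**5. Scale of the stated hazard.** In the data that Section 10 cites, mean progesterone rose from 0.38 to 2.17 ng/ml at this trial's dose, in nine participants of whom eight were men. Against the postmenopausal ceiling of 0.7, 2.17 / 0.7 = 3.1. Against the lower luteal bound of 3.3, 2.17 / 3.3 = 0.66. The level was therefore above the postmenopausal range and below the luteal range.

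**6. The history clause.** The same sentence claims exclusion by personal and family history of any of the five disorders. Section 7 lists family history for one kind of condition only: "Personal or first degree family history of known hormone sensitive tumors". Section 11 repeats this for estrogen-sensitive tumors. Family history of clots, pulmonary embolism, heart attack or dementia is not listed.

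**7. Power.** None of the inputs in Section 15 is an age. The planned 144 and the stated 90% power do not depend on which limit is right.

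**The case against.** The strongest reply is that Section 6 is clear and governs, so staff know whom to randomize. On this view Section 10 merely carries one uncorrected number. The cited harms followed years of combined hormones, whereas this trial gives 16 weeks of treatment and bars hormone therapy. Section 7 screens for cardiovascular, clotting and tumor risk, and hormone levels are measured.

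Most of this stands, and it keeps the severity low. It would support a decision to keep 67. It does not make the Section 10 statement true, and the documents do not show that 67 is the intended limit: the only place that derives an age limit from the hazard gives 62.

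A reader might infer more than the text supports:

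- **That women over 62 have been enrolled or harmed.** The documents give no enrolment data, and they do not show whether sites have been applying 62 in practice.
- **That the threefold excess over the postmenopausal ceiling shows a serious hazard.** Section 10 itself says that the level was below the luteal range, and it rests on very few women.
- **That family-history screening is absent.** The documents show only that it is not listed. The claim in Section 10 can be read as a loose summary, and clinician judgment remains available under Section 7.

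**Conclusion.** The conflict is real and unreconciled in the current text: a stated safety exclusion is missing from the operative eligibility rule. Its size is five years of age, in a group narrowed by the menopausal-stage requirement and of unknown number. The conclusion assumes only that Sections 6 and 7 are the criteria to which Section 4 refers and that age is counted in whole years. It does not extend to the primary analysis or to power. The mismatch over family history is minor and adds little. This should be fixed, at the low end of severity.

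**What to change.** The sponsor should first establish which limit is intended and check enrolment status, which the documents do not give. One IRB amendment then makes Sections 6 and 10 agree.

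- **If 62 is the intended safety limit:** set Section 6 to 40 to 62 for further enrolment, and report how many women over 62 have already been randomized under the limit of 67. The cost is narrower recruitment. The loss is probably slight, given the stage requirement, but the documents do not allow it to be estimated. The stated power holds if 144 is still reached.
- **If 67 is intended:** delete the over-62 exclusion from Section 10 and state why ages 63 to 67 are acceptable. Possible grounds are the 16-week exposure, the bar on hormone therapy, the Section 7 cardiovascular, clotting and tumor exclusions, and progesterone expected below the luteal range, with the thin data in women acknowledged. The text should not present 67 as following from the cited harms, because nothing in the protocol derives it from them. The cost is wording only, provided that sites have been working to 67.

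In either case, reword the history clause in Section 10 to match what Section 7 lists. New family-history exclusions are not needed for this fix.

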The likely risks from the study are primarily medication side effects and the risk of untreated depressive symptoms. As with the UTSW research group's prior pregnenolone studies, an IND application will be filed with the FDA. Pregnenolone is considered by the Food and Drug Administration (FDA) as an over-the-counter (OTC) supplement, and extensive literature suggests that its side effects are generally mild and comparable to those of placebo. Pregnenolone appears to be well tolerated; however, all participants will receive a safety and tolerability assessment (mental status exam, mood symptoms, suicidality, and side effects) by a study psychiatrist and a research coordinator at each study visit. Although the available data suggest that pregnenolone administration does not alter estrogen levels, women with a history of estrogen sensitive tumors or a first degree relative (e.g. mother, sister) with estrogen sensitive tumors will be excluded.

At study completion, participants will be instructed on how to taper and discontinue the study drug (pregnenolone or placebo) over one week (150 mg twice a day (BID) x 4 days, 50 mg twice a day (BID) x 4 days, discontinue), and will also be given referral information for the local treatment facilities. If needed, we will provide a longer period of aftercare until treatment can be transitioned to another provider. A final telephone safety phone call will also be scheduled after the end of study participation. If a participant informs the research team that she would like to discontinue the study, every effort will be made to schedule a final in-clinic appointment, during which all assessments for Weeks 8 or 16 (depending on the time of discontinuation) will be conducted.

Another potential risk is worsening of mood symptoms. If participants have a worsening of mood symptoms, such as active suicidal or homicidal ideation with clear plan and the intent to act on the plan, study participation will be discontinued and follow-up treatment will be arranged. Some level of suicidal ideation is common in participants with depressive symptomatology, thus recurrent suicidal thoughts accompanied by a clear understanding that the participant does not plan to act on these thoughts (as assessed and documented by a study clinician) would not require discontinuation. In general, in the event of a medical or psychiatric emergency (e.g., active suicidal ideation), appropriate medical advice will be provided, including recommendations for emergency room evaluation if necessary. [name] and other UTSW physicians involved with the study have staff privileges at the Parkland and William P. Clements University Hospital Emergency Rooms, which are likely to be the most commonly used hospitals by the participants. In addition, [name] and the MGH study staff will be conducting study procedures on the same hospital campus as the MGH Emergency Rooms and Acute Psychiatric Service if appropriate medical attention is warranted. In the event of an acute medical emergency, the researchers will also be able to summon medical assistance either by calling the Rapid Response Team for the clinic or calling 911.

An investigator will be available 24 hours a day. The consent form will have both daytime and nighttime numbers for reaching study personnel. Business cards for the research coordinator and psychiatrists will also be provided. In the event an investigator or research coordinator is on vacation or out-of-town, coverage will be provided, and both the research coordinator and UT Southwestern answering service are informed of the name and pager number of the physician on-call. The MGH Triage line will page the study physician on-call.

Potential pharmacokinetic or pharmacodynamic drug-drug interactions will be managed using inclusion, exclusion, and discontinuation criteria and dose adjustments. Clinical assessments are collected by trained and experienced staff members who will be able to reassure participants if they are distressed during study visits. If participants become fatigued or stressed during the testing, rest periods will be provided. Standard, appropriate measures will be used to minimize risk of infection during venipuncture.

All women of childbearing potential (as outlined in the inclusion/exclusion criteria) must have a urine pregnancy test with negative results prior to receiving study medication. These participants will also be asked to use effective forms of contraception and dates of last menstrual period during the study. Pregnancy or failure to use contraceptives will result in discontinuation from the study.

Potential safety concerns will result in discontinuation from the study protocol. However, standard care will be provided until referral to another physician for further care can be arranged. Examples of these safety concerns are given below:

- Development of active suicidal or homicidal ideation with plan and intent, clear and progressive worsening of psychiatric symptoms that in the opinion of the investigator makes continued care within the research study unsafe, or development of psychotic features
- Development of severe or life-threatening medical condition, pregnancy or psychiatric hospitalization
- Withdrawal of informed consent by the participant

These are general guidelines. Additionally, clinician judgment, as well as specific discontinuation criteria, will be used to determine whether or not a participant can safely remain in the study.

12. Data Management and Monitoring

At the beginning of the study, a REDCap database will be set up by the Dallas site in collaboration with the Boston site. Original data (including PHI) will be maintained at the site of collection (Dallas or Boston). However, de-identified data used in the data analysis (e.g., depressive symptoms) will be stored centrally using the secure electronic REDCap system. These data will be reviewed recurrently by the Dallas data monitor and any errors or inconsistencies will be discussed. A data monitor from both the Dallas and Boston sites will review data charts and corresponding digital database content weekly and provide feedback to the PIs and research staff on data quality and recommend remediation, if necessary.

An independent Data and Safety Monitoring Board (DSMB) will be formed to oversee the progress of this clinical trial. The board will provide an independent review and oversight mechanism for the study and will meet immediately prior to the initiation of enrollment in the study and again at least twice per year, as per National Institute of Aging (NIA) guidelines. The researchers will present safety data to the board for review, including changes in psychiatric symptom severity and side effects. In addition, materials provided to the IRBs, including serious adverse events leading to death or hospitalization will be forwarded to board members. The board will review preliminary data on adverse events and outcomes. If the board feels that protocol modifications are needed, it will have the authority to recommend modifications of safety procedures and recommend temporary or permanent discontinuation of enrollment. However, the final decision on these safety matters will rest with the institutional IRBs and NIH. The suggested DSMB plan will be approved by NIH prior to study enrollment.

13. Procedures to Maintain Confidentiality:

The patient records from the research study and the executed consent forms will be maintained in locked file cabinets in one of the PI's offices on campus. All data will either be maintained in locked file cabinets or on computers with password-protected access. We will not disclose information about individual patients in the study without the patient's consent. A certificate of confidentiality will be obtained.

14. Potential Benefits:

The primary benefit of the study will be to determine whether pregnenolone therapy will improve depressive symptoms and anxiety. Based on our pilot data, some participants may benefit from the study. However, the primary goal is to obtain information that will benefit future patients. All patients in the study will receive a thorough assessment and careful longitudinal monitoring of depressive symptoms. The medication selected (pregnenolone) appears to be generally safe and well-tolerated. We feel it is essential for this study that a placebo group be included as the efficacy is not well established. Thus, the benefits of the study are great and will include a better understanding of the treatment of depressed patients. We believe that the risks, though clearly present, are greatly outweighed by the benefits of this study.

15. Power Analysis & Sample Size Determination

The sample size calculation was performed using a customized program in SAS (v9.2), and was based on the SPCD sample size formula that takes into account the mean treatment effect

combined with equal weighting of each stage-wise estimate and its variance, and subject retention rates for the trial. We assume 67% placebo non-responders in Stage 1, 10% dropout rate for Stage 1 and 5% dropout in Stage 2. The sample size calculation was performed for a continuous response assuming a Stage 1 mean change from baseline to Week 8 in total MADRS score between pregnenolone and placebo of 3.5 (standard deviation (SD) of 8) and a Stage 2 difference of 5 (SD=8). Given these assumptions, a sample size of 144 subjects (randomized in 2:1 ratio at Stage 1 for placebo and pregnenolone) will have 90% power to detect a change from baseline in total MADRS score between pregnenolone and placebo. This assumes a two-sided hypothesis test with 0.05 significance is used for the comparison between pregnenolone and placebo.
